3.0 Objectives

Our overarching hypothesis is that MyPath will increase patient-centered reproductive planning discussions and improve contraceptive decision quality, leading to improved reproductive behaviors and health outcomes for women Veterans receiving primary care at VA. To test this hypothesis, we will conduct a randomized controlled trial (RCT) at up to 16 sites, clustered at the provider level among up to 100 providers and their reproductive-aged women Veteran patients, guided by the following aims:

Aim 1. To test the effect of MyPath on the occurrence of reproductive planning discussions with SDM (primary outcome), compared to usual care. Secondary outcomes include the impact of MyPath on communication self-efficacy and measures of contraceptive decision quality (knowledge, decisional conflict, values concordance).

Aim 2. To test the effect of MyPath on clinical outcomes at 3 and 6 months after the index visit including contraceptive utilization (continuous contraceptive use, use of effective methods) and unintended pregnancy, compared to usual care. Exploratory outcomes will include behaviors to modify preconception health risks.

Aim 3. To identify potential barriers and facilitators to implementation by collecting process and cost data and conducting qualitative interviews with Veterans, providers, and clinic leaders, with the goal of facilitating future implementation in partnership with Women's Health Services if MyPath is found to be effective.

Exploratory analyses will also look for effect modification of Aim 1 and 2 outcomes by race/ethnicity, age, visit modality (in-person or virtual) and provider practice-type (Women's Clinic or non-Women's Clinic).

In addition, we plan to obtain covariate and outcome data in VA Corporate Data Warehouse (CDW) from the electronic health record to collect some demographic and covariate variables and inform future implementation studies. We will compare self-reported reproductive health outcomes of participants (collected at 3- and 6-months) with reproductive health data from the

electronic health record to assess for agreement and identify possible CDW structured data that would be used as outcomes for larger-scale implementation studies.

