5.0 Study Procedures

5.1 Study Design

Experimental Design

For Aims 1, and 2, we will use a cluster randomized trial design with clustering at the provider level to study the efficacy of MyPath delivered via text message to patients prior to primary care appointments at VA. The unit of randomization is the provider. This approach allows us to optimize efficiency while minimizing the risk of bias and contamination. Specifically, randomizing providers rather than patients addresses the contamination concern that providers interacting with patients who use MyPath may be exposed to the Summary Page from the tool highlighting patients' goals and preferences, which could alter communication with patients who have not used the tool.

After enrollment, providers will be randomized to **intervention arm** or **usual care arm** with a 1:1 allocation ratio. Randomization will be stratified by the clinic practice-type (Women's Clinic vs. non-Women's Clinic) and study site (Seattle, Salt Lake City, Pittsburgh, and the additional non-engaged PBRN sites: Atlanta, Denver, Durham, Houston, Orlando, San Diego, Amarillo, Central Texas, El Paso, South Texas, North Texas, Texas Valley Coastal Blend, and West Texas). We will include stratification by clinic practice-type because we expect providers located in Women's Clinics may communicate about reproductive planning differently than providers in other primary care settings.

Women Veterans will be identified for recruitment if they have a scheduled primary care appointment with an enrolled study provider, are 18-44 years old, and have no CDW evidence of impaired decision-making or a past procedure that would result in infertility (e.g., hysterectomy, oophorectomy, or sterilization). Those patients will be screened, consented, and enrolled approximately one week before their scheduled appointment. Recruitment will take place over the course of 18 months.

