Intervention: The MyPath intervention is designed to promote guideline-recommended care and best practices for reproductive health care. As such, MyPath itself is a variation of usual practice. Providers randomized to the intervention arm will receive the link to the MyPath tool, a brief orientation to MyPath by telephone, a brief conversation guide (Attachment T), and a wearable button (Attachment U) and card (Attachment V) prompting patients to bring up MyPath during their appointment. Study staff may also identify and send publicly available clinical resources for reproductive health counseling or decision making when requested. Study staff will contact providers in the intervention arm approximately every six months (via phone, email or MS Teams message) to provide updates on the study and offer support and advice regarding the MyPath tool. Providers in the control/usual care arm will not be provided any education or information about the intervention, will be asked not to disseminate MyPath to their patients during the study recruitment phase, and will provide usual care.

Enrolled patients scheduled to see intervention providers will be sent a text message prior to their appointment through the existing national VA VetText program (see letter of support from [name] IIR grant application, Attachment B). The text message will include a brief invitation to use MyPath along with a link to the tool. Participants will be asked whether they consent to receive text messages from VA that include PHI, a practice that the VetText program uses to be able to send additional details about appointments in text messages. Participant consent will be documented in their study record. In the MyPath pilot study, patients spent an average of 11 minutes using the MyPath tool. The MyPath tool can be accessed at va.mypathtool.org using a mobile device or Google Chrome web browser. Screens shots from each main section of MyPath may be reviewed in the attached MyPath Intervention Overview (Attachment C).

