Patients: Veteran participants may benefit in several ways from the study. From [name] previous work, women Veterans of childbearing age generally perceive significant gaps in care related to pregnancy planning and contraception counseling in VA primary care. In prior qualitative work, Veterans were enthusiastic about efforts on the part of VA to improve these services. Women Veteran participants may benefit from knowing that they are contributing to research efforts to improve delivery and quality of VA care. Women Veteran participants in the study intervention arm may benefit by knowledge gained, improved quality of their reproductive decisions, improved communication with their providers, and improved health behaviors after using the MyPath tool. Women Veterans in the control arm will not benefit from the MyPath intervention during the study but could benefit from implementation after the study, if the intervention is found to be effective. Veteran participants will also receive monetary incentives to compensate their time.

Balance of Potential Risks and Benefits: These potential benefits outweigh the minimal risks related to loss of privacy and confidentiality and of discomfort when discussing health or operational matters, which are no greater than those encountered by employees and VA patients in daily life.

Protection for Vulnerable Populations

All VA employees will be informed that their participation is voluntary and that opting out will not affect their employment, work environment, or benefits in any way.

It is likely that patients from vulnerable populations will be included in our datasets, such as employees or students; economically and/or educationally disadvantaged persons; and patients who identify as racial/ethnic minorities. We do not anticipate the intervention or participation in the study evaluations will pose any additional risks to these populations. Should members of these groups be included, we anticipate that they will be adequately protected by the above strategies of risk minimization.

Data Repository/Data Banking

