5.5 Study Evaluations

Providers:

Screening: During screening, we will determine whether potentially eligible providers meet the eligibility criteria for participation in the study by reviewing inclusion and exclusion criteria. The list of provider screening variables is included as part of the attached Provider Survey Instrument (Attachment R).

Demographic and Practice Characteristics Survey: Providers complete a brief demographic and practice characteristics survey prior to randomization. The list of demographic and practice characteristics variables is attached as part of the Provider Survey Instrument (Attachment R).

Aim 3 Qualitative Interview: After completion of patient enrollment, intervention arm providers who participate in the qualitative interview will be invited to do a 15-20 minute qualitative interview. During the interview, providers will be asked questions about their experience providing care to women receiving the MyPath intervention and facilitators and barriers to implementing MyPath in clinical practice (see attached interview guide, Attachment S).

Patients:

Screening: During screening, we will determine whether potentially eligible patients meet the eligibility criteria for participation in the study by reviewing inclusion and exclusion criteria. We will ask additional screening questions in service of obfuscating the specific purpose of the study until after patients have attended their medical appointment (as discussed above in section 5.3). All screening questions are detailed in the Patient Survey Instruments (Attachment Q).

Intervention: Intervention arm participants will be asked questions after their scheduled visit about whether they accessed and used the MyPath website prior to their visit. They will also be assigned a personal code at the start of the MyPath tool. We will then ask participants to provide the personal code at the post-visit survey so that we can obtain analytic information on their use of the tool after the fact. Analytics collected using this method will include the length of time the patient stayed on the MyPath webpage, which modules they used, and whether or not they navigated to the MyPath summary page. MyPath can be viewed at va.mypathool.org and the MyPath Intervention Overview (Attachment C) includes example screen shots from each main section of the web-based intervention.

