
Please complete this survey for “Improving Outcomes for Women Veterans”:
 
[Link to Qualtrics Survey]
 
Questions? Call 206-XXX-XXXX

Reminder: Submit your next survey to help improve women Vets’ healthcare:
 
[Link to Qualtrics Survey]
 
Questions? Call 206-XXX-XXXX

Reminder: Submit survey to support women’s health at VA and receive \$50:
 
[Link to Qualtrics Survey]
 
Questions? Call 206-XXX-XXXX

Please complete VA women’s health study survey by MM/DD to receive \$50:
 
[Link to Qualtrics Survey]
 
Questions? Call 206-XXX-XXXX

Reminder: Help the VA improve care for women Vets and receive \$50:
 
[Link to Qualtrics Survey]
 
Questions? Call 206-XXX-XXXX

All survey questions assessed at each timepoint are provided in the attached Patient Survey Instruments (Attachment Q) and summarized below.

- Baseline survey: Demographics, pregnancy intentions, and whether the patient is at risk of unintended pregnancy (UIP) will be assessed. Baseline preconception health risks will be assessed.
- Post-visit survey: The primary outcome of the occurrence of a reproductive planning discussion with SDM and the secondary outcomes of communication self-efficacy and family planning knowledge will be assessed among all participants. Secondary outcomes relating to contraceptive choices and decisions will also be assessed post-visit among the subgroup at risk of UIP. Whether participants discussed preconception health risks or received any services related to preconception health risks identified at baseline will be assessed among participants considering pregnancy. At the end of the post-visit survey we will ask questions related to use of the intervention for Aim 3, including collecting the users’ assigned personal codes as described above.
- 3- and 6-month surveys: Changes in pregnancy goals and whether the patient continues to be at risk of UIP will be assessed. Secondary outcomes relating to contraceptive use and unintended pregnancy will be assessed among the group remaining at risk of UIP. Preconception health behaviors, an exploratory outcome, will be assessed.

Aim 3 Qualitative Interview: Intervention arm patients who participate in the qualitative interview will be asked questions about their experience receiving the MyPath text message, using or not using the MyPath intervention, and using any other similar health-related tools previously (see interview guide, Attachment S).

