Aim 2 Secondary Outcomes: Secondary outcomes for Aim 2, including continuous contraceptive use, consistent contraceptive use, and unintended pregnancy, will be assessed at 3- and 6-month follow up **in the subgroup at risk of UIP**. We will use a mixed effects logistic regression model to test whether outcomes differ between groups. For continuous and consistent contraceptive use outcomes, we will adjust for self-reported pre-study contraceptive use (measured at the post-visit survey).

Exploratory Preconception Health Behaviors: These outcomes will be assessed among a subgroup of study participants considering pregnancy in the next few years or who are ambivalent about pregnancy (unsure). Preconception risk factors will be measured at baseline and using medical record data, and behaviors to modify those risk factors will be assessed at post-visit, 3-months, and 6-months.

Exploratory Analyses of Interaction Effects: **For Aim 1 and 2 outcomes**, we will assess modification of the effect of assignment to the intervention by the following 4 pre-specified factors: age, race/ethnicity, visit modality (in-person or virtual) and clinic type (Women’s Health Clinic yes/no). We will assess evidence for effect modification by adding the effect modifier and its interaction with the treatment assignment indicator to the primary analysis models specified above.

Exploratory Analyses of Patient-Centered Contraceptive Outcomes: Recognizing that pregnancy intentions may fluctuate and participants in the subgroup at risk of UIP may decide that they wish to pursue pregnancy during the study timeframe, we will create “goals-concordant” measures for both continuous contraceptive use over 6 months and consistent contraceptive use at 6 months. Goals-concordant continuous contraceptive use will be defined as non-continuous use among women who desire pregnancy now; any continuous use outcome among women who are not trying but would be okay with pregnancy; and continuous use among women who desire pregnancy later, never, or who are not sure. Goals-concordant

consistent contraceptive use will be defined as no method or inconsistent use among women who desire pregnancy now; no method, inconsistent use or consistent use among women who are not trying but would be okay with pregnancy; and consistent contraceptive use among women who desire pregnancy later, never, or who are not sure.

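### The request that control providers hold back MyPath lapses when recruitment closes, up to six months before Aim 2 follow-up ends, and later use by controls would apparently go unseen

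*Combined protocol and SAP*

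**What the plan says.** **The request.** Section 5.1 (Intervention) says that control providers receive no training or details on MyPath, that they deliver usual care, and that they "will be asked not to disseminate MyPath to their patients during the study recruitment phase".

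**The timetable.** Section 5.1 (Experimental Design) states: "Recruitment will take place over the course of 18 months". Patients are "enrolled approximately one week before their scheduled appointment". Section 3.0 defines Aim 2 in terms of "clinical outcomes at 3 and 6 months after the index visit". Section 5.6 repeats this for the subgroup at risk of unintended pregnancy (UIP): "continuous contraceptive use, consistent contraceptive use, and unintended pregnancy, will be assessed at 3- and 6-month follow up".

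**The expectation for controls.** The risk-benefit part of section 5.1 says "Women Veterans in the control arm will not benefit from the MyPath intervention during the study". It goes on to allow that they may gain from a later roll-out if the tool proves effective.

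**The measurement of use.** Under the patient intervention heading, section 5.5 says "Intervention arm participants will be asked questions after their scheduled visit about whether they accessed and used the MyPath website prior to their visit". Its survey summary says "At the end of the post-visit survey we will ask questions related to use of the intervention for Aim 3". The same summary lists the 3- and 6-month content as pregnancy goals, continuing UIP risk, contraceptive use, unintended pregnancy and preconception behaviours. It lists no question on MyPath use.

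**The concern.** The trial randomises providers partly to keep the comparator clean, and Aim 2 is framed as a comparison with usual care. The one instruction that keeps control providers from passing on the tool ends with recruitment, while outcomes are still accruing for patients enrolled late. Nothing elsewhere in the protocol extends it. The operating rule in section 5.1 therefore does not secure the expectation, in the risk-benefit text of the same section, that controls stay unexposed for the whole study.

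Control use during follow-up would pull the Aim 2 differences toward zero. If use is not recorded, the investigators could not say how much of a small or null Aim 2 difference came from exposure of controls. The secondary causal analysis of actual use in section 5.6 would also lack exposure data for the follow-up period.

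**Working it through.** **1. The plan's own figure.** The inputs in section 5.6 are 50% versus 70%, two-sided 5%, 80% power, 30% non-use in the intervention arm, coefficient 0.01, about 15 patients per provider and 5% attrition.

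- Per arm, pooled variance: [1.960 × √(2 × 0.6 × 0.4) + 0.842 × √(0.5 × 0.5 + 0.7 × 0.3)]² / 0.20² = 93.0
- Non-use: 93 / (1 − 0.30)² = 189.8
- Clustering: 189.8 × [1 + (15 − 1) × 0.01] = 189.8 × 1.14 = 216.4
- Attrition: 216.4 / 0.95 = 227.8, so 228 per arm and **456 in total**

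The stated N is reproduced. It rests on the post-visit primary outcome, so each patient's contribution is measured before her follow-up begins. The gap does not touch this calculation.

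**2. Patients assessed after the request ends.** Assume uniform accrual over 18 months and 228 controls, and ignore the week between enrolment and visit, which would raise these figures slightly.

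- 6-month assessment after close of recruitment: 6/18 = 1/3; 228 × 1/3 = **76**
- 3-month assessment after close of recruitment: 3/18 = 1/6; 228 × 1/6 = **38**
- At the enrolment cap of 570 (285 controls), the 6-month figure is 285 × 1/3 = 95

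These counts come before two reductions. Section 5.6 assumes 20% attrition at follow-up, which would leave about 76 × 0.80 = 61 and 38 × 0.80 = 30. The contraceptive and pregnancy outcomes are then limited to the UIP subgroup, whose size the documents do not give.

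**3. Share of follow-up time uncovered.** In the last third of accrual, the uncovered part of the 6-month window runs from none to all of it and averages one half: 1/3 × 1/2 = **1/6** of all control follow-up time.

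**4. Whether later use would be seen.** The only point at which section 5.5 places use questions is the post-visit survey. The personal codes that link web analytics to a patient are described in sections 5.1, 5.5 and 7.0 for the intervention group, and are collected at that same survey. On this description, use by a control after the post-visit survey would not be captured. That holds for every control, not only for those enrolled late.

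**The case against.** The strongest reply is that an expired request is not permission. Control providers get no link, orientation, conversation guide, button or card, and the protocol plans no release of MyPath when recruitment closes. This stands, and it is why the likely extent is small.

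Four stronger readings are tempting, and the documents do not support them.

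- *That section 5.1 contradicts itself.* The sentence about control women is a risk-benefit statement, not an operating rule. The instruction to providers is narrower and fails to secure that statement, but the two are not in conflict.
- *That control use is never measured.* Section 5.5 describes use questions for intervention participants. However, the Blinding text in 5.1 and the survey summary in 5.5 can be read as asking all patients after the visit, and section 5.6 foresees crossover. Attachment Q, which holds the full items, was not available. What can be said is that the summary lists no use item at 3 or 6 months.
- *That the open web address, the debrief or the clinic-leader interviews show exposure starting when the request ends.* The address is the same throughout. The debrief reaches controls whenever they enrolled, and whether it names the tool depends on Attachment P, which was also unavailable. The interviews seek views, and no dissemination is described.
- *That the Aim 2 effect shrinks by a known amount.* If 10% to 30% of the late third used MyPath with full effect, against 70% use in the intervention arm, the loss would be (1/3 × 0.10)/0.70 = 4.8% to (1/3 × 0.30)/0.70 = 14.3%. No uptake figure is given in the documents. Full effect is also implausible for women whose index visit has passed and who lacked the provider materials.

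**Conclusion.** The gap is real, and the wording of section 5.1 creates it. The request to control providers ends with recruitment, and Aim 2 follow-up of the last patients runs about six months longer. Under uniform accrual, about a third of controls at 6 months and a sixth at 3 months are assessed after it lapses, with about a sixth of control follow-up time uncovered. Later use by any control would apparently go unseen, subject to the contents of Attachment Q.

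The amount of contamination cannot be estimated from the documents. Any bias is toward no difference and is confined to the Aim 2 secondary outcomes and the exploratory follow-up outcomes. The primary outcome and the N of 456 stand. This is a cheap improvement: low severity, medium confidence.

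**What to change.** In section 5.1 (Intervention), change the end point of the request to control providers from the recruitment phase to: *until the last enrolled patient has completed the 6-month survey*. This brings the rule into line with the risk-benefit text.

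Add one MyPath-use question for both arms as the last item of the 6-month survey, after all outcomes, so that naming the tool cannot affect the responses already given. Report control-arm use beside the Aim 2 results. The question also covers controls who find the tool on their own, which the longer request cannot prevent.

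The cost is one phrase in the protocol, the matching wording given to control providers, and one survey item. The downside is that control providers wait about six more months before they may share the tool.

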Quantitative: Quantitative data collection to assess reach will include intervention adherence by patient participants (i.e., the proportion of patients in the intervention arm who used the intervention). Analytic data from the software developers hosting MyPath will be obtained. Analytic data will verify self-reported use of the tool, quantify time spent using the tool, and describe which pages of MyPath are most visited to better understand the reach of MyPath among women receiving the intervention. Women in the intervention group will be assigned a personal code consisting of two words and a number when they access MyPath, and MyPath analytic data will be linked to this code. Linkage of the code will be maintained in a crosswalk behind the VA firewall. Lastly, process data will be collected to estimate costs of implementing the intervention, including time spent training intervention arm providers, costs of disseminating the tool, and costs of software

Study Population

Providers: We will enroll up to 100 primary care providers who have seen at least 30 unique reproductive-aged women in the past year. Providers will be recruited across the 9-16 study sites. Trainees who must staff with attending providers (e.g. residents and medical students) will be excluded from participation. After patient recruitment is complete, we will invite intervention arm providers to complete qualitative interviews for Aim 3 about their experiences seeing patients who used the tool.

Patients: We anticipate enrolling approximately 456 women Veteran patients (not to exceed 570 patients) scheduled to see enrolled providers over the course of 18 months of recruitment. We aim to recruit approximately 15 patients scheduled to see each study provider, for a cluster size of 15 and a total sample size of 456, though depending on enrollment rates and in efforts to balance the number of patients in study arms, additional patients may be enrolled up to a maximum of 570. Up to 30 intervention arm Veteran participants will be interviewed for Aim 3. They will be purposively sampled for variety in characteristics such as intervention adherence, race/ethnicity, age, parity, provider in a women's clinic vs non-women's clinic, and site/geographic location.

Clinic Leaders: We will enroll and interview up to 20 clinic leaders who work with enrolled providers for Aim 3.

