Recruitment letters will include a study information statement for patients (Attachment J) and a postage-paid opt-out postcard (Attachment K) which patients may return by mail if they do not wish to be contacted further about study participation. The data requisitioner will pull lists of potentially eligible patients assigned to enrolled provider primary care panels again at 6 and 12 months into the patient recruitment phase and recruitment letters will be mailed to any new patients (those not previously mailed a recruitment letter). The study manager and research coordinator will track any opt-out postcards in the patient crosswalk database so that no further contact will be made with those patients.

During the active patient recruitment phase of the study, the data requisitioner will pull weekly lists of potentially eligible VA patients (same criteria as above) that are scheduled to see enrolled study providers during the following week. In-person, telephone, and video-conferencing appointments will be eligible study visits. The study manager, research coordinator, or database manager will match these lists against the patient crosswalk database to remove any patients to whom a recruitment letter was never sent, who returned the opt-out postcard, who already enrolled in the study, or who have declined participation or withdrawn from the study previously.

Those vetted recruitment lists will be distributed to the study RAs, who will make contact with patients prior to their appointments by email (for screening, when email addresses are available) and subsequently by telephone (for screening, consent and enrollment; see attached script, Attachment L).

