5.6 Data Analysis

Aims 1 and 2 - Sample Size:

Sample size and power calculations are based on our primary outcome, occurrence of reproductive planning discussion between patient and provider with shared decision making (SDM), and rely on formulas specified for use in cluster randomized trials accounting for non-use of the tool in the intervention group and attrition.[39] We estimate that the baseline prevalence of discussions of contraception and/or preconception health among women who could potentially become pregnant will be 50%, based on estimates from the nationally-representative VA ECUUN study and our pilot study.[2] Based on field testing, we estimate that 30% of women participants enrolled in the intervention arm who receive the text with the MyPath link will not actually view the tool and the sample size calculation will thus account for this estimated non-use. Assuming a kappa coefficient of 0.01 and attrition of 5%, a sample of 456 patients (approximately 15 patients for each of 30 providers) will yield 80% power in 2-sided tests with a type-1 error rate of 5% to detect a 20-percentage point increase in reproductive planning with SDM to 70%. This difference is clinically meaningful and consistent with what we observed in our pilot (22% increase).

Aims 1 and 2 - Missing data and subject dropouts:

For the 3- and 6-month follow-up periods, we assume 20% attrition (15% lost to follow up and 5% who either become pregnant or change to desiring pregnancy). This is a conservative estimate based on 7% attrition at 3-months in our pilot. All appropriate efforts will be made to avoid missing data, including monitoring of missingness and subject dropout rates by the PI and study manager or research coordinator biweekly during the study data collection phase. The research coordinator will investigate causes and remedies. For key analysis variables that have 15% or more missing values, we will analyze factors that are associated with having a missing value and perform a sensitivity analysis using multiple imputation to allow an unbiased analysis for all subjects.

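### The permission to enrol beyond 456 in order to balance patient numbers between arms has no stated rule and could make entry to the trial depend on arm, with no enrolment-period term in the primary model

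*Combined protocol and SAP*

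**What the plan says.** Section 5.1 (Experimental Design) makes the provider the unit of randomisation, with 1:1 allocation: "Randomization will be stratified by the clinic practice-type (Women's Clinic vs. non-Women's Clinic) and study site". Patients are identified and enrolled afterwards, over 18 months.

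Section 5.1 (Study Population) aims for about 15 patients per provider and 456 in total. It allows more for two reasons. One is enrolment rates; the other is balance: "in efforts to balance the number of patients in study arms, additional patients may be enrolled up to a maximum of 570". The Abstract calls 456 a minimum, and section 5.2 repeats the cap of 570. No trigger, decision-maker, method or closing rule for balancing is given.

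In section 5.2, "the data requisitioner will pull weekly lists of potentially eligible VA patients (same criteria as above) that are scheduled to see enrolled study providers" in the following week. The study manager, research coordinator or database manager vets these lists before the research assistants receive them. Section 5.1 (Blinding) keeps the assistants unaware of provider arm and of which patient sees which provider. It says nothing about the blinding of those who vet the lists. Table 3 in section 6.0 names the study manager or research coordinator as a reviewer, every two weeks, of tool use in the intervention group.

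Section 5.6 analyses the primary outcome with a mixed effects logistic model. The covariates include study site, practice type and visit type; calendar time and enrolment period are absent.

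**The concern.** In a cluster trial that recruits patients after the clusters are randomised, the arms stay comparable only if patients enter by the same process in both. Patients cannot be moved between arms here. Deliberate balancing of patient numbers therefore works only by recruiting harder, or for longer, from providers in the smaller arm. Whether a woman is enrolled would then depend partly on her provider's arm.

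Blinding the research assistants limits their selection of individual women. It does not stop lists being steered by arm before they reach the assistants, and some of the roles that vet the lists also see arm-specific information.

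If the added patients came late and mainly from one arm, any change over time in reproductive counselling that the listed covariates do not capture would be mixed with the treatment effect on the primary outcome.

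**Working it through.** **Inputs from section 5.6.** Control rate 50%, intervention rate 70%, two-sided 5% test, 80% power, 5% attrition, about 15 patients for each of 30 providers. Non-use: "30% of women participants enrolled in the intervention arm who receive the text with the MyPath link will not actually view the tool". The kappa of 0.01 is read as the intracluster correlation, because that reading reproduces the plan's total. The caps of 456 and 570 are from section 5.1. The arm splits and drift values below are assumptions.

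**1. The plan's own figure.** Per arm, n = [1.96√(2 × 0.6 × 0.4) + 0.8416√(0.5 × 0.5 + 0.7 × 0.3)]² / 0.20² = 93.0, so 186 in total.
- Non-use: 186 / 0.70² = 379.6
- Clustering: × [1 + (15 − 1) × 0.01] = × 1.14, giving 432.7
- Attrition: / 0.95, giving 455.5

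The stated 456 is reproduced. No power argument is given for 570.

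**2. What equal arms are worth at a fixed 456.** Variance ratio = (1/a + 1/b) / (2/228), an individual-level approximation.
- 210:246 gives 1.006
- 200:256 gives 1.015
- 180:276 gives 1.046

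**3. Exposure if a balancing top-up were late and one-armed.** Bringing the smaller arm up to the larger arm L makes the total 2L. With a cap of 570, L is at most 285, so the most extreme start is 171:285. Late share = (L − S)/L, where S is the smaller arm. Shift in the arm difference = late share × drift.

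| Start | Added | Late share | Shift (points) for a drift of 5 / 10 / 15 points |
|---|---|---|---|
| 210:246 | 36 | 36/246 = 14.6% | 0.7 / 1.5 / 2.2 |
| 182:274 | 92 | 92/274 = 33.6% | 1.7 / 3.4 / 5.0 |
| 171:285 | 114 | 114/285 = 40.0% | 2.0 / 4.0 / 6.0 |

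For scale, the plan's 20-point effect diluted by 30% non-use is 0.70 × 20 = 14 points by intention to treat.

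**4. What extra patients are worth.** Power = Φ[(0.14 − 1.96 × SE0)/SE1], with n′ = 0.95n analysed per arm, 15 providers per arm and design effect D = 1 + (n′/15 − 1) × 0.01.
- SE0² = 0.24 × (D₁/n′₁ + D₂/n′₂)
- SE1² = 0.21 × D₁/n′₁ + 0.25 × D₂/n′₂, with arm 1 the intervention arm

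At 228:228, n′ = 216.6, D = 1.134, SE0 = 0.0501 and SE1 = 0.0491, so power is 80.2%. The arm-neutral column keeps the starting split at the same final total. The intervention arm is taken as the larger; reversing this changes the starting powers by less than half a point.

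| Start at 456 | Power | Smaller arm topped up to equality | Same total, arm-neutral |
|---|---|---|---|
| 251:205 | 79.8% | 251:251 (502), 83.4% | 276:226, 83.0% |
| 274:182 | 78.6% | 274:274 (548), 86.1% | 329:219, 84.7% |
| 285:171 | 77.7% | 285:285 (570), 87.2% | 356:214, 85.2% |

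**5. Cost of unequal arms at the same total.** With p and q the two arms' shares of patients, 1/(4pq) gives 1.010 at 55:45, 1.042 at 60:40 and 1.067 at 62.5:37.5.

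**The case against.** The best case for the plan is that it describes no arm-directed recruitment. The weekly lists are drawn from all enrolled providers, and the listed removals (no letter sent, opted out, already enrolled, declined or withdrawn) include no arm filter. Enrolment rates are the first reason given for going past 456, and 456 is elsewhere a minimum, so exceeding it is ordinary planned enrolment. A single 18-month window covers everyone. Applying the 15-per-provider target equally would also tend to even out the arms without anyone looking at arm.

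Most of this stands, and it rules out several stronger readings that a reader might infer.
- **That a late, one-armed top-up is the procedure.** The text does not say that one arm closes or that the extra patients come last. This is a possible consequence of an unstated rule.
- **That going past 456 gains almost no precision.** That is true only of balance at a fixed total. Adding patients helps even when it unbalances the arms: 228:342 against 228:228 gives (1/228 + 1/342)/(2/228) = 0.833, a 17% fall in variance.
- **That 114 women could be added to an arm of 228 for balance.** That would create imbalance. A balancing top-up of 114 needs a 171:285 start.
- **That the stratification is undone, or that site mix and visit modality go unadjusted.** Providers remain allocated as stratified, and site, practice type and visit type are in the primary model.

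The objection does not remove the balancing purpose itself. It is written into section 5.1, it has no rule, and enrolment period is not modelled.

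**Conclusion.** The point holds as a gap that should be closed, not as a demonstrated bias. The plan permits enrolment after randomisation to be steered by running arm totals, does not say how, and has no enrolment-period term to absorb residual change in counselling over time.

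If the steering were late and one-armed, an assumed 10-point drift would move the arm difference by about 1.5 points (210:246 start) to 4 points (171:285 start). The documents give no evidence of any drift, and its sign and the arm topped up would set the direction. These figures also assume that the smaller arm is brought exactly to equality and that all added patients are late.

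Balance buys little in return. Even at 274:182, power at 456 is 78.6% against 80.2% for equal arms. The real gain comes from the larger total, and arm-neutral recruitment keeps most of it: 84.7% against 86.1% at 548, and 85.2% against 87.2% at 570.

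**What to change.** In section 5.1, delete the phrase about balancing patient numbers between arms. State instead that any recruitment beyond 456, up to 570, uses the same list criteria and the same per-provider cap for all enrolled providers in both arms, and closes on one date for both.

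If arm-directed enrolment has already occurred, flag those patients. Report a sensitivity analysis of the primary outcome that either adjusts for enrolment period or is restricted to the period when both arms were recruiting.

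The cost is one sentence in the protocol and, if needed, one sensitivity analysis. The arms may end unequal, which costs about 1–7% in variance for splits from 55:45 to 62.5:37.5. The option to go to 570 is kept.
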